### **8.12. Occupational Exposure**

An occupational exposure occurs when, during the performance of job duties, a person (whether a healthcare professional or otherwise) gets in unplanned direct contact with the product, which may or may not lead to the occurrence of an AE.

An occupational exposure is reported to safety within 24 hours of the investigator's awareness, using the SAE Report Form, regardless of whether there is an associated AE/SAE. Since the information does not pertain to a subject enrolled in the study, the information is not reported on a CRF; however, a copy of the completed SAE Report Form is maintained in the study master file.

### **8.13. Withdrawal Due to Adverse Events (See Also [Section 6.10 Subject Withdrawal](#))**

Withdrawal due to AE should be distinguished from withdrawal due to other causes according to the definition of AE noted earlier, and recorded on the appropriate AE CRF page.

When a subject withdraws because of an SAE, the SAE must be reported in accordance with the reporting requirements defined below.

### **8.14. Eliciting Adverse Event Information**

The investigator is to report all directly observed AEs and all AEs spontaneously reported by the study subject or subject's parent(s)/legal guardian. In addition, each study subject or subject's parent(s)/legal guardian will be questioned about AEs.

### **8.15. Reporting Requirements**

Each AE is to be assessed to determine if it meets the criteria for SAEs. If an SAE occurs, expedited reporting will follow local and international regulations, as appropriate.

### **8.15.1. Serious Adverse Event Reporting Requirements**

If an SAE occurs, Pfizer is to be notified within 24 hours of investigator awareness of the event.

In particular, if the SAE is fatal or life-threatening, notification to Pfizer must be made immediately, irrespective of the extent of available AE information. This time frame also applies to additional new information (follow-up) on previously forwarded SAE reports as well as to the initial and follow-up reporting of exposure during pregnancy and exposure via breastfeeding cases and occupational exposure cases.

If the investigator is aware of an SAE with an onset on the day of investigational product administration or during the calendar day following investigational product administration, the investigator must contact the Pfizer study physician directly immediately after sending the SAE Report Form to Pfizer. These procedures do not replace any of the standard SAE reporting requirements as described above. Additional information can be found in the SRM.

In the rare event that the investigator does not become aware of the occurrence of an SAE immediately (eg, if an outpatient study subject initially seeks treatment elsewhere), the investigator is to report the event within 24 hours after learning of it and document the time of his/her first awareness of the AE.

For all SAEs, the investigator is obligated to pursue and provide information to Pfizer in accordance with the time frames for reporting specified above. In addition, an investigator may be requested by Pfizer to obtain specific additional follow-up information in an expedited fashion. This information collected for SAEs is more detailed than that captured on the AE case report form. In general, this will include a description of the AE in sufficient detail to allow for a complete medical assessment of the case and independent determination of possible causality. Information on other possible causes of the event, such as concomitant medications, vaccines, and/or illnesses, must be provided. In the case of a subject death, a summary of available autopsy findings must be submitted as soon as possible to Pfizer or its designated representative.

SAEs are to be reported throughout the study from signing of the ICD up to the study end (Visit 7: Month 12 Follow-up and Blood Draw).

At Month 12 (Visit 7: Month 12 Follow-up and Blood Draw), the site will inquire about SAEs, newly diagnosed chronic medical conditions, or medically attended events (AEs that resulted in evaluation at a medical facility) since Visit 6.

### **8.15.2. Nonserious Adverse Event Reporting Requirements**

All AEs will be reported on the AE page of the CRF. It should be noted that the form for collection of SAE information is not the same as the AE CRF. Where the same data are collected, the forms must be completed in a consistent manner. For example, the same AE term should be used on both forms. AEs should be reported using concise medical terminology on the CRFs as well as on the form for collection of SAE information.

Nonserious AEs will be reported from the signing of the ICD to up to Visit 6 (Post-Vaccination 3 Blood Draw).

Nonserious AEs starting between Visits 6 and 7 will only be reported in the CRF if they are either a newly diagnosed chronic medical condition or a medically attended event that resulted in evaluation at a medical facility since Visit 6.

At all visits, particular care must be taken to note any neuroinflammatory and autoimmune conditions, such as transverse myelitis, uveitis, optic neuritis, and multiple sclerosis.

At all visits, stop dates for any reported AEs that were ongoing at the previous visit will be recorded in the CRF. The investigator must instruct on the need to report AEs during this time period.

The investigator must contact the Pfizer study physician directly as soon as possible after becoming aware of an AE that required medical attention that began on the day of investigational product administration or during the calendar day following investigational product administration. These procedures do not replace any of the standard [AE Reporting Requirements](#) as described above. Additional information can be found in the SRM.

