#### **6.7. Visit 6 (28 to 42 Days After Visit 5): Post–Vaccination 3 Blood Draw**

- Ensure that the subject continues to be eligible for the study, meets none of the withdrawal criteria ([Section 6.10](#)), and meets none of the temporary delay of blood draw criteria ([Section 4.4](#)).
- Collect the subject's e-diary.
- Review the subject's e-diary data since the previous visit and follow up on any ongoing reactogenicity or use of antipyretic medication.

- Complete the Study Visit AE Checklist to:
  - Inquire whether the subject had any newly diagnosed chronic medical conditions since the last visit. Inquire whether the subject had any of the following related to an AE since the last visit: hospitalizations, visits to other medical facilities, medication use, or missed days of school (if appropriate). Please refer to the SRM for additional details.
  - Inquire about neuroinflammatory and autoimmune conditions, such as transverse myelitis, uveitis, optic neuritis, and multiple sclerosis. Please refer to the SRM for additional details.
- Record AEs as described in the AE [Reporting Requirements](#) section and the [Schedule of Activities](#).
- Review AEs that were ongoing since the previous visit and record their end dates or confirm that they are still continuing.
- Record concomitant medications used to treat AEs as described in the Concomitant Treatment section ([Section 5.8](#)).
- Record nonstudy vaccinations as described in the Concomitant Treatment section ([Section 5.8](#)).
- Provide the subject's parent(s)/legal guardian with a memory aid. Instruct the parent(s)/legal guardian to use the memory aid between Visits 6 and 7 to remind them to review any significant illnesses, hospitalizations, newly diagnosed medical conditions, or AEs that resulted in evaluation at a medical facility with study site personnel. Please refer to the SRM and [Section 7.2](#) for additional details.
- Collect a blood sample (approximately 5 mL for subjects aged  $\geq$ 24 months to  $<$ 4 years at the time of blood draw and approximately 10 mL for those aged  $\geq$ 4 years at the time of blood draw) from the subject. Collect the blood sample only if the subject meets none of the temporary delay of blood sample collection criteria described in [Section 4.4](#).
- Ask the parent(s)/legal guardian to contact the investigator immediately if any significant illness or hospitalization occurs.

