### **8.3. Reporting Period**

For SAEs, the active reporting period to Pfizer or its designated representative begins from the time that the subject provides informed consent, which is obtained prior to the subject's participation in the study, ie, prior to undergoing any study-related procedure and/or receiving investigational product, through and including 6 months after the last administration of the investigational product. SAEs occurring to a subject after the active reporting period has ended should be reported to the sponsor if the investigator becomes aware of them; at a minimum, all SAEs that the investigator believes have at least a reasonable possibility of being related to investigational product are to be reported to the sponsor.

A subject's AEs (serious and nonserious) will be reported and recorded from the signing of the ICD through Visit 6.

At Month 12 (Visit 7: Follow-up and Blood Draw), the site will inquire about SAEs, newly diagnosed chronic medical conditions, or AEs that resulted in evaluation at a medical facility since Visit 6.

At all visits, particular care must be taken to note any neuroinflammatory and autoimmune conditions, such as transverse myelitis, uveitis, optic neuritis, and multiple sclerosis.

At Visit 7, the site will inquire about any AEs, as well as RRIs ([Section 8.2](#)), for events occurring during the 48-hour period after blood draw. These events must be recorded in the CRF for the visit at which the blood was drawn and the event must be followed.

At all visits, stop dates for any reported AEs that were ongoing at the previous visit will be recorded in the CRF. The investigator must instruct the parent(s)/legal guardian on the need to report AEs and SAEs during this time period.

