5. ANALYSIS SETS

5.1. Full Analysis Set

The intent-to-treat (ITT) population includes all subjects who are randomized. All randomized subjects who have at least 1 valid and determinate assay result related to a proposed analysis will be included in the modified intent-to-treat (mITT) population. This analysis set is for the immunogenicity analysis. Subjects will be analyzed according to the investigational product to which they were randomized.

5.2. 'Per Protocol' Analysis Set

The evaluable population will be the primary population for the immunogenicity analyses. To be included in the evaluable population for the primary immunogenicity endpoint, subjects will have to meet all the following criteria:

1. Randomized into the study,
2. Were eligible, ie, satisfied all inclusion/exclusion criteria, through 1 month post vaccination 3,
3. Received all the scheduled investigational products at study visits 1, 3 and 5 as randomized,
4. Have baseline blood drawn prior to the first dose of vaccine and have post-vaccination 3 blood draw (Visit 6) within 28-42 days after vaccination 3 (Visit 5). (The interval day will be calculated as blood draw date – vaccination date),
5. Had a valid and determinate assay results for the proposed analysis, and
6. Had no important protocol deviations.

An important protocol deviation is a protocol deviation that, in the opinion of the sponsor's global medical monitor, would materially affect assessment of immunogenicity, eg, subject receipt of a prohibited vaccine or medication that might affect immune response or a medication error with suspected decrease in potency of the vaccine. The sponsor's global medical monitor will identify those subjects with an important protocol deviation before any immunogenicity analysis is carried out.

Subjects will be analyzed according to the investigational product to which they were randomized.

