6.2.3.1. Analysis Intervals

There will be up to 7 analysis intervals for safety data collected via CRF.

Table 9. Analysis Interval for AE, SAE, Medically Attended AE and Newly Diagnosed Chronic Medical Conditions

#	Analysis Interval	Analysis Population	Interval Start date (inclusive)	Interval Stop (inclusive)	Safety Data
1	Within 30 days after vaccination 1	Vax 1 Safety	Vax 1 date	Vax 1 date + 30 days	AE, SAE, MAE, NDCMC
2	Within 30 days after vaccination 2	Vax 2 Safety	Vax 2 date	Vax 2 date + 30 days	AE, SAE, MAE, NDCMC
3	Within 30 days after vaccination 3	Vax 3 Safety	Vax 3 date	Vax 3 date + 30 days	AE, SAE, MAE, NDCMC
4	Within 30 days after any vaccination	Safety	Vax 1, Vax 2, or Vax 3 date	Vax 1, Vax 2, or Vax 3 date + 30 days	AE, SAE, MAE, NDCMC
5	During the vaccination phase	Safety	Visit 1 date	Visit 6 date (or end of vaccination day)	AE, SAE, MAE, NDCMC, Days missed school due to AE
6	During the follow-up Phase	Follow-up Safety	Visit 6 date + 1 day, or end of vaccination date + 1 for early withdrawal subjects	Visit 7 date	SAE, MAE, NDCMC,
7	Throughout the study	Safety	Visit 1 date	Visit 7 date	SAE, MAE, NDCMC, Neuroinflammatory and autoimmune conditions

AE=Adverse events, SAE=Serious adverse events, MAE=Medically-attended AE, NDCMC=Newly diagnosed chronic medical conditions

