8.2.5.2.4. Immediate AE

The number and percentage of subjects reporting adverse events during the protocol specified first 30-minute observation period will be summarized by group for each vaccination.

This immediate AE report will be summarized for each vaccination and any vaccination. These summaries will include 95% Clopper-Pearson's CI. Unconditional exact 95% CI on the proportion differences and p-value will also be provided.

The immediate AE categorized as SAE (defined as immediate AE and also meet the definition of SAE) will be summarized similarly.

Immediate AE will not be summarized by preferred term. Instead, these immediate AE will be listed.

8.2.5.2.5. AE

The AEs will be analyzed similar as per [Section 8.2.5.2.1](#), except that only the first 5 intervals from [Table 9](#) are applicable as regular (nonserious, not medically attended) AEs are only collected during the vaccination phase. However, if such AEs during the follow-up phase were recorded in the database, these data will be listed separately.

Note that for the analysis interval of vaccination phase the AEs will be summarized by each preferred term (MedDRA) with percentage and number of events for each group.

Percentages and 95% CIs on the proportion differences will also be provided for adverse events with 1% or above.

In addition, related AEs will also be summarized by each preferred term with percentage and number of events for each group.

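### A Visit 6 on day 28 or 29 after dose 3 ends ordinary nonserious AE collection one or two days short of the 30-day AE interval, so the dose-3 AE percentage is slightly understated

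*Protocol*

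**What the plan says.** **Endpoint.** Protocol 2.2.2 and SAP 6.2.1 make the percentage of subjects with at least one AE a primary safety endpoint, over 30 days after each vaccination, 30 days after any vaccination, and the vaccination phase.

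**Analysis interval.** SAP 6.2.3.1, Table 9, gives AE among the data for row 3 (dose 3) and row 4 (any dose). Row 3 stops at "Vax 3 date + 30 days", with start and stop dates inclusive. Row 4 stops 30 days after whichever dose applies. Row 5, the vaccination phase, stops at the Visit 6 date, and row 6, the follow-up phase, starts the day after.

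**Collection.** Protocol 8.3: "A subject's AEs (serious and nonserious) will be reported and recorded from the signing of the ICD through Visit 6". Protocol 8.15.2 agrees: "Nonserious AEs will be reported from the signing of the ICD to up to Visit 6 (Post-Vaccination 3 Blood Draw"). It then restricts what is recorded later: "Nonserious AEs starting between Visits 6 and 7 will only be reported in the CRF if they are either a newly diagnosed chronic medical condition". The other exception is for events that were medically attended. SAEs are collected to Visit 7.

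**Visit window.** The Schedule of Activities and Protocol 6.7 place Visit 6 "28 to 42 Days After Visit 5". SAP 5.2 fixes the day count: "The interval day will be calculated as blood draw date – vaccination date".

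**Late entries.** SAP 8.2.5.2.5 applies the first five Table 9 intervals to AEs, because ordinary AEs are collected only in the vaccination phase, but adds: "if such AEs during the follow-up phase were recorded in the database, these data will be listed separately".

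**The concern.** The endpoint needs ordinary AEs through day 30 after dose 3, yet a fully compliant Visit 6 can close their collection on day 28. The dose-3 figure, and the any-dose figure through its dose-3 part, would then carry a 30-day label without 30 days of collection for some children, and the plan asks for no count of how many.

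There are two side effects. Ascertainment inside the interval becomes mixed: after a day-28 visit, a medically attended AE on day 29 is recorded and an ordinary AE that day is not. And if an ordinary AE from day 29 does reach the database, its handling is unclear. By date it belongs to row 3, but it also falls in the follow-up phase, which 8.2.5.2.5 sends to a separate listing. Such entries are plausible, because the Visit 7 checklist (Protocol 6.8) asks about AE-related medication and missed school since Visit 6. Two programmers could produce different primary safety tables.

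**Working it through.** The 30-day interval is a definition, so there is no derived figure to reproduce. The check compares it with the collection that the visit schedule guarantees.

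**1. Days lost per child.** Day counts are date minus vaccination date. The interval covers days 0 to 30, which is 31 dates. Shortfall = max(0, 30 − Visit 6 day).

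| Visit 6 day | Dates covered | Days lost | Share of interval |
|---|---|---|---|
| 28 | 29 of 31 | 2 | 2/31 = 6.5% |
| 29 | 30 of 31 | 1 | 1/31 = 3.2% |
| 30 to 42 | 31 of 31 | 0 | 0 |

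**2. Doses 1 and 2.** Collection continues to Visit 6. The minimum after dose 1 is 42 + 105 + 28 = 175 days, and after dose 2 it is 105 + 28 = 133 days. Both exceed 30.

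**3. Share of children affected.** The documents give no attendance by day. *Assumption:* uniform over the 15 permitted days. Then 2/15 = 13.3% are affected, about 53 of 400 (40 of 300 and 13 of 100). Mean loss is (2 + 1)/15 = 0.2 day, and 0.2/31 = 0.65% of the interval. If 5% to 50% attended on day 28 or 29, the count would be 20 to 200 of 400.

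**4. Effect on the dose-3 percentage.** *Assumptions:* constant hazard, all AEs ordinary, and every affected child losing 2 days. The last two push the estimate upward. With true 30-day risk p, an affected child's observed risk is 1 − (1 − p)^(29/31). Understatement = share affected × (p − observed risk).

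| True p | Observed, affected child | Gap, points | Share 2/15 | Share 50% |
|---|---|---|---|---|
| 10% | 9.39% | 0.61 | 0.08 | 0.31 |
| 30% | 28.37% | 1.63 | 0.22 | 0.81 |
| 50% | 47.71% | 2.29 | 0.30 | 1.14 |

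**5. Effect on the any-dose percentage.** The three intervals cannot overlap under the visit windows (dose 2 at least 42 days after dose 1, dose 3 at least 105 days after dose 2), so row 4 spans 3 × 31 = 93 days, and a day-28 visit loses 2/93 = 2.2%. With exponent 91/93 and the same assumptions, the gap for an affected child is 0.20 points at an any-dose risk of 10% and 0.75 points at 50%. Multiplied by 2/15 this is 0.03 to 0.10 points; by 50%, 0.10 to 0.38 points.

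**6. Against sampling error.** At an assumed 30% risk, the normal-approximation 95% half-width is 1.96 × √(0.3 × 0.7/300) = 5.2 points for Group 1 and 1.96 × √(0.3 × 0.7/100) = 9.0 points for Group 2.

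**7. Does any other provision close the gap?** Protocol 8.3 has an inquiry about AEs in the 48 hours after blood draw, which would cover days 29 and 30 if it applied to a day-28 Visit 6 draw. It does not: Protocol 8.2 limits the research-related-injury provision to Visit 7, and SAP 8.2.5.3 ties it to that visit. No text stops rows 3 and 4 at Visit 6 for AEs, and none extends ordinary AE collection to day 30.

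**The case against.** The strongest reply is that this is a labelling matter with almost no effect on results, and much of it stands.

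- **Coverage.** A reader might infer that the 30-day window goes unobserved for these children. It does not: at least 29 of 31 dates are covered, and on the rest SAEs, medically attended AEs and new chronic conditions are still collected.
- **Group comparison.** A reader might infer that it is biased. Protocol 9.5 and SAP 8.1.2.2 speak generally of comparing AE endpoints, but SAP 8.2.5.2.1, which 8.2.5.2.5 follows, provides differences and Fisher p-values only for the vaccination phase and the whole study, and the latter does not apply to ordinary AEs. The vaccination phase ends at Visit 6, exactly where collection ends. Both groups also share the visit window.
- **Dose 3 against doses 1 and 2.** A reader might infer that a planned comparison fails. No such AE comparison is specified.
- **A 6.5% loss.** That is one child's lost time after a day-28 visit, not bias in a percentage of children with at least one event.
- **SAP self-contradiction.** This is too strong. Section 8.2.5.2.5 does not say that an event inside row 3 is removed from it. The text is ambiguous and needs a sentence.

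What does not fall away is that the schedule fails to guarantee the interval stated for a primary safety endpoint, and that the SAP does not settle which late entries count.

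It can also be objected that opening Visit 6 at day 30 would set the protocol window against the 28-to-42-day evaluability rule. That is met by stating in SAP 5.2 that an early draw stays evaluable.

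**Conclusion.** The mismatch is real and minor. For children seen at Visit 6 on day 28 or 29, ordinary nonserious AEs go uncollected for the last two days or last day of the interval in Table 9 row 3, and of the dose-3 part of row 4. The dose-3 AE percentage is understated by about 0.1 to 0.3 points under uniform attendance and a true risk of 10% to 50%, and by up to about 1 point if half attend early. The any-dose percentage is understated by less. These sizes rest on an assumed attendance pattern and a constant hazard, since the documents supply neither. They are small beside the sampling error of each group's percentage.

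The SAE, medically attended AE and chronic-condition endpoints and the vaccination-phase comparison are unaffected, so the documents do not support reading this as a threat to the safety conclusions. Separately, SAP 8.2.5.2.5 is unclear on whether an ordinary AE recorded after Visit 6 but within 30 days of dose 3 is counted or only listed.

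**What to change.** Reconcile Protocol 6.7, 8.3 and 8.15.2 with SAP Table 9 and 8.2.5.2.5.

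**If Visit 6 visits are still to come:** open the Visit 6 assessment window at day 30 in the Schedule of Activities and Protocol 6.7. The shortfall is then zero for every in-window visit. Keep SAP 5.2 at 28 to 42 days and state that an earlier draw remains evaluable. The cost is an amendment and 13 rather than 15 scheduling days.

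**If the visits are done:**

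- Keep rows 3 and 4 at 30 days after dose 3, and count every recorded AE in that interval, including SAEs and medically attended AEs after Visit 6.
- State that this overrides the separate listing in 8.2.5.2.5.
- Report by group the number of children with Visit 6 before day 30.
- Repeat the row 3 and row 4 AE percentages in children with Visit 6 on day 30 or later, as a descriptive check.

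The cost is a short SAP clarification and one additional table, with a smaller denominator (about 13/15 × 400 = 347 under uniform attendance).

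**Do not truncate rows 3 and 4 at Visit 6 for AEs.** That would discard SAEs and medically attended AEs on days 29 and 30 that were collected, and could leave the any-AE percentage below that of its own medically attended subset.
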